****MAIN RESEARCH QUESTIONS, STUDY AIMS, SPECIFIC HYPOTHESES****

1.1 Please clearly state your overall research questions and/or study aims.

Primary Research Question:

Does combining the use of Integra®, a synthetic dermal substitute, with the application of a skin graft, known as autografting, into a one-stage procedure result in comparable outcomes to the standard two-stage procedure, so as to be a feasible, safe alternative to the standard two-stage approach?

Primary Hypothesis:

Single-stage Integra reconstruction is safe, i.e. does not result in increased infections, and effective, i.e. does not result in increased graft loss, justifying further study in small to intermediate-sized burns that could result in significantly reduced hospital stays in a specific burn population.

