Post-operatively, the patient's care would be largely unchanged. Progress of graft "take" at the single-stage 125cm² site would be monitored regularly. Eventually, 10-14 days later, the patient would return to the operating room for eventual auto-grafting over their standard Integra®. If autograft "take" at the single-stage site was poor, the area would be regrafted. If graft "take" at the single-stage site was adequate, the area would not require additional surgery. Thus, the total number of surgeries would not be expected to change, as the patient will require two trips to the operating room regardless of trial enrollment. The 125 cm² site would be monitored daily after dressing "take-down" (typically post-operative day 5) while hospitalized and then on a standard post-operative schedule for sloughing or graft loss, infection, hematoma or underlying blood collection, seroma or underlying fluid collection, and time to 95% healed. This last variable is measured by determining the post-operative day at which 95% of the surface area of the graft is covered with epidermis. Because we are meshing the 40 cm² sheet of skin in a 3:1 fashion, the resultant graft will look like a thin fence of skin with open diamond-shaped interstices that will slowly each fill in from the peripheral surrounding skin as the graft heals. It is these interstices that give the typical meshed appearance of healed skin grafts. When 95% of the open areas have filled in, that day is determined to be the time to 95% healing. Similarly, an adjacent area of identical size, which will be treated in the standard fashion, will be monitored serially and will serve as a control. Since patients will serve as their own controls, a direct comparison between reconstruction strategies will be enabled.

Not Applicable

Eligible patients will be adults (Age 18 or older) admitted to the Regions Hospital Burn Center with thermal burns that will be reconstructed with Integra®. There is not a firm protocol in place for Integra® use – this is decided at the level of the burn attending physician on a case-by-case basis.

2.3 What is the study population of interest and what are the study inclusion/exclusion criteria?

Inclusion criteria – English-speaking adult burn patients greater than 18 years old, admitted with burn injuries eligible for Integra® reconstruction at the discretion of the burn attending physicians.

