****3. ANALYSIS****

3.1 Describe the statistical methods that will be used to address the study aims. For each aim, this will usually include:

- Description of the sample used for the particular analysis
- The variables included in the specific analysis and their role in the analysis
- Numeric summaries computed (e.g., mean, standard deviation, proportion, correlation)
- A summary of data exploration and presentation activities (e.g., generating scatter plots, summary tables)
- Description of statistical tests (e.g., independent samples t-test, Mann-Whitney test), and models constructed (e.g., logistic regression)

Please see our **Examples of Statistical Methods**.

Describe here:

Note: Please reference the area/pages of an established protocol if you are not writing your own analysis plan.

This is a descriptive pilot study. Means and standard deviations will be computed to describe continuous variables and percents for binary or categorical variables. Patient demographics (age, sex) will be tabulated to characterize the population.

Aim 1 will be to describe the time to 95% healing of the single-stage reconstructed skin graft as well as to determine the frequency of complications of infection, seroma, hematoma, sloughing, and graft loss. Aim 2 will be to compare that to the same characteristics of the adjacent (control) 125 cm² skin graft.

Frequency charts for incidences of complications between the single-stage and control skin grafts will be compared with chi-square tests. Times to 95% healing will be compared with t-tests.

Sample size:

3.2 What is the estimated sample size(s) for the primary study analyses (per group for studies with different arms or comparison groups)?

We plan to evaluate this procedure in 10 patients.

3.3 The sample size selected was (check all that apply):

	Based on data likely to be available during a specific time period (often based on data available in past periods)
	To conduct one or more specific analyses with adequate statistical power
	To achieve a specified level of precision in one or more key estimates
x	Other (explain): This is a descriptive study

3.4 Explain your choice of the sample size selection you listed above:

This is a pilot study – we believe we can enroll 10 patients in a 6 month timeframe and present our results at a regional and/or national conference to proceed with a multi-institutional study.

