3.5 Describe your assumptions concerning data available for analysis (e.g. How many subjects will be randomized, possibly lost to follow-up or a procedure? What do you expect for survey response rates, and how much missing data do you expect?). Include information as it pertains to your study (human or animal).

We don't believe any patients will be lost to follow-up, as we will be excluding patients based on this limitation. We expect to have sufficient follow-up data on at least 90% of patients as our post-surgical clinic follow-up rates are above 90%.

Power analysis

NOTE: If you are doing a descriptive study (i.e., aside from computing confidence intervals you are not using statistical tests, inferential statistical testing for group comparisons, or statistical models), please complete 3.6 and skip 3.7-3.8.

If you are conducting statistical tests, using statistical inference to compare groups, or are building statistical models, please skip 3.6 and complete 3.7-3.8. **Please see our Example Power Analysis**.

3.6 Provide a measure of the precision of your estimates for key study endpoints, (e.g., 95% confidence intervals on proportions or means), using actual expected estimates.

This study will be descriptive.

We believe that there will be no increase in graft loss or delayed time to healing, but do not have a precision measure of this information. Our results will be precisely described our findings.

- 3.7 What level of differences observed in your primary endpoints would be considered clinically or practically significant?
- 3.8 What is the power for your primary analysis (and the set of assumptions underlying it: hypothesis addressed, expected pattern of effects with justification for these expectations, analysis used, variables in the analysis, effect sizes, sample sizes, alpha level, one or two-sided test)?

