3.9 What are the limitations of the proposed approach and analysis?

The limitations are precisely that this is a descriptive pilot study based on a total of 10 patients. While we will characterize our data accurately, this will not be a large enough study, nor will we be auto-grafting a large enough area to extrapolate single-stage reconstruction of large burns. However, should the procedure be deemed safe and effective, it would serve as a springboard to a multi-institutional study involving single-stage reconstruction of small burns, with the definition of "small" to be determined.

3.10 Please name the people who completed the analysis section of this application.

[name]

3.11 Please name the people who will summarize data and conduct statistical analysis.

[name]

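### The hypothesis is no increase in infections or graft loss, but the plan offers only difference tests in 10 patients; even 0/10 versus 0/10 leaves an increase of up to 28 points open

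*Combined protocol and SAP*

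**What the plan says.** Section 1.1 asks whether one-stage reconstruction gives outcomes comparable to the two-stage standard. It hypothesises that "Single-stage Integra reconstruction is safe, i.e. does not result in increased infections, and effective, i.e. does not result in increased graft loss".

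The design in section 2.1 is paired: each patient has one single-stage site and one adjacent control site of the same size. "Since patients will serve as their own controls, a direct comparison between reconstruction strategies will be enabled".

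Section 3.1 gives the analysis. "Means and standard deviations will be computed to describe continuous variables and percents for binary or categorical variables". Then "Frequency charts for incidences of complications between the single-stage and control skin grafts will be compared with chi-square tests", and healing times are compared with t-tests. No confidence interval is planned. Section 3.2 sets the sample at 10 patients, and section 3.4 bases that number on enrolment feasibility.

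On precision, section 3.6 says the team expects no increase in graft loss and no delay in healing, "but do not have a precision measure of this information". The form's note above section 3.6 tells applicants who use statistical tests, "or are building statistical models, please skip 3.6 and complete 3.7-3.8". Sections 3.7 (important difference) and 3.8 (power) have no answer.

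Section 3.9 states: "The limitations are precisely that this is a descriptive pilot study based on a total of 10 patients". It continues that, "should the procedure be deemed safe and effective, it would serve as a springboard to a multi-institutional study". It does not say what result would lead to that judgement.

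**The concern.** The hypothesis asserts that there is no increase, while the planned tests take no difference as the null. Failing to reject that null is the expected outcome in a sample this small, whether or not the new procedure does harm. A non-significant p-value could therefore be read as support for the hypothesis when it carries almost none.

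The judgement of safety and effectiveness is the stated step to a multi-institutional study. Without an interval, those planning that study cannot see which increases the 10 pairs have excluded. The plan also has it both ways on the form: it specifies tests, but answers as a descriptive study and then gives no precision either.

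**Working it through.** **Inputs.** n = 10 pairs (sections 2.1 and 3.2). Possibly 9 evaluable, since section 3.5 expects sufficient follow-up in at least 90%. Tests as in section 3.1. The documents give no confidence level, alpha, margin or control event rate. Two-sided 95% and 0.05 are assumed below, and control rates are shown over a range. The sample size has no calculation behind it, so there is no figure of the plan's to reproduce.

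**Paired risk difference (single-stage minus control), Tango score interval.** Let b be the pairs with an event at the single-stage site only and c those with an event at the control site only. The limits are the values of d that solve

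|b - c - n·d| / sqrt(n·(2q + d(1 - d))) = 1.96,

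where q is the constrained maximum-likelihood estimate of the control-only probability. With b = c = 0, q is 0 and the solution is d = z²/(n + z²) = 3.84/13.84 = 0.278.

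| Events (control, single-stage) | b, c | Paired 95% interval |
|---|---|---|
| 0/10, 0/10 | 0, 0 | -27.8 to +27.8 points |
| 1/10, 3/10, control case also a single-stage case | 2, 0 | -13.3 to +51.0 points |
| 1/10, 3/10, control case not a single-stage case | 3, 1 | -21.7 to +55.1 points |

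The unpaired Newcombe interval for 1/10 versus 3/10 is -16.0 to +51.4 points. For 0/10 versus 0/10, the upper limit is 28.8 points by Miettinen-Nurminen. With 9 pairs the score limit is 3.84/12.84 = 29.9 points.

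**What the planned chi-square would report (no continuity correction).**
- 1/10 versus 3/10: p = 0.264.
- 0/10 control: 3/10 gives p = 0.060 and 4/10 gives p = 0.025.
- 1/10 control: 5/10 gives p = 0.051 and 6/10 gives p = 0.019.
- 0/10 versus 0/10: the statistic is undefined, so the result most favourable to the hypothesis produces no test.

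**Chance of detecting a true tripling.** Full enumeration of two independent binomials with n = 10 each, two-sided 0.05:

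| Assumed control rate | Single-stage rate | Power |
|---|---|---|
| 5% | 15% | 3% |
| 10% | 30% | 14% |
| 20% | 60% | 42% |
| 30% | 90% | 82% |

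**Single-site exact (Clopper-Pearson) 95% limits.** For zero events the upper limit is 1 - 0.025^(1/n).
- 0/10: 30.8%.
- 0/9: 33.6%.
- 1/10: 0.3% to 44.5%.

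**Healing time.** The half-width of the 95% interval for the mean paired difference, in units of the SD of the differences, is t(0.975, n-1)/sqrt(n). That is 2.262/3.162 = 0.72 for 10 pairs and 2.306/3 = 0.77 for 9.

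**The case against.** The strongest reply is that this is a declared descriptive pilot. The hypothesis sentence goes on to say that the result would justify further study, and section 3.9 concedes the sample size. Holding 10 patients to a non-inferiority margin would be out of proportion. That stands, and it limits the severity. It does not remove the no-increase hypothesis or the tests. A purely descriptive study is also exactly where section 3.6 asks for precision. What section 3.9 concedes is that the study cannot be extrapolated to large burns; it does not say that 10 pairs cannot show no increase.

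Further points have some force:
- The 28-point figure depends on method. A one-sided 95% score limit for 0/10 versus 0/10 is 2.706/12.706 = 21 points; two-sided methods give 28 to 29 (up to 31 if the single-site exact limit is used). None of these would support a claim of no increase.
- At 0/10 versus 0/10 there is no p-value to misread. The 1/10 versus 3/10 case shows the misreading; the zero-event case shows that only an interval can report what remains open.
- The power figures rest on assumed rates and independent sites, although the sites are paired. They illustrate the problem, and the conclusion does not need them.
- Graft coverage is also recorded as a percentage (section 2.8). The risk-difference figures apply to graft loss only if it is scored yes or no per site.
- A single-stage site with poor take is regrafted at the second operation (section 2.1), so its healing time may not be a clean observation. The half-width assumes a usable time for every pair.
- The text between sections 3 and 5 was not available for this review. A criterion stated only there cannot be excluded, but the analysis answers where it belongs contain none.

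**Conclusion.** The concern holds, with high confidence. It is a change that should be made, but it does not undermine the pilot. The planned analysis cannot support the stated hypothesis: the best possible observed result still leaves an increase of up to 28 percentage points compatible with the data, and a threefold observed rate (1/10 versus 3/10) is non-significant with an upper limit above 50 points. The 28-point figure needs only n = 10, a yes/no outcome per site and a two-sided 95% score interval. The consequence is limited because the next step is another study, not adoption of the procedure.

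**What to change.** - **Section 3.1:** make estimation the analysis. For infection, graft loss and each other complication, report the count at each site with an exact 95% interval, the paired 2x2 table, and the paired risk difference (single-stage minus control) with a 95% score interval. For healing time, report the mean paired difference with a 95% interval and the number of pairs contributing. Label any p-values exploratory.
- **Section 3.6:** replace the statement that no precision measure exists with the n=10 figures: 0/10, upper limit 30.8%; 1/10, 0.3% to 44.5%; 0/9, upper limit 33.6%; no events at either site, difference -28 to +28 points; healing time, half-width 0.72 SD of the paired differences.
- **Sections 1.1 and 3.9:** state that a non-significant result is not evidence of no increase, and restate the claim as feasibility plus observed rates with intervals.
- **Section 3.9, secondary:** if the safe-and-effective wording stays as the step to the further study, say in advance what observed result it means. The study team sets this.

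The cost is a little more analysis and new wording in four sections. No extra patients are needed. The price is a less favourable claim.

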****1. BACKGROUND & SIGNIFICANCE****

1.2 What is the specific knowledge gap that the project intends to fill? Include a brief review of past research in this area, numbering your citations to relevant literature as well as including them in the reference section #9.1.

Integra®, a synthetic dermal substitute, has been utilized in burn care for decades.¹ Composed of a porous collagen-chondroitin 6-sulfate fibrillary mat covered with a thin sheet of silastic, it serves to cover wound beds of freshly excised burns and allow for the infiltration of fibroblasts, capillaries, and macrophages, essentially creating a "neodermis" while also acting as a barrier against infection and a blockade against heat and moisture loss.¹ Typically, 10-14 days after Integra® placement, a patient returns to the operating room, the top silastic layer of the Integra® is removed, and an autograft — a split-thickness skin graft harvested from the patient — is applied directly on top of the incorporated Integra®. The result is regarded to be a cosmetically and functionally superior result to that which would have been obtained had the wound bed itself been autografted at the time of excision, as opposed to being covered by Integra® and autografted during a second operation.

Advantages of Integra® use are several.

- There are cosmetic advantages and functional advantages to the end result when compared with grafting alone.^{2,3}
- Integra® provides a temporary infection and moisture loss barrier until the definitive coverage with the split-thickness skin graft. This divides the overall reconstruction, and, therefore, the associated physiologic insult into two stages. It should be noted that this advantage did not start with the invention of Integra® homograft and allograft (cadaver) coverage provided temporary coverage prior to the advent of Integra®.
- The neodermis allows for definitive coverage to be done with a thinner split-thickness skin graft than would otherwise be utilized to cover an Integra®-free wound bed. This allows for faster donor site healing with decreased scarring and pain. Additionally, in the setting of larger burns, the faster donor site healing means a shorter time until these donor sites can be re-harvested to cover additional burned sites.

Disadvantages of Integra® include infection risk, the need for an additional surgery, the cost of Integra® itself, and the increased hospital length of stay necessitated by waiting for the additional surgery, although this latter point has been brought into question in severely burned patients.⁴

Integra® use in single-stage procedures to cover defects without grafting has shown benefit when defects are fairly small, e.g. fingertip injurires⁵, and small head and neck skin cancer resections. Single-stage resection, Integra® placement and autografting has been successfully utilized in the setting of upper extremity avulsion injuries and was utilized in the burn setting as mentioned in a 2012 letter to the editor published in *Burns*. This aforementioned letter to the editor mentions a single-case. To our knowledge no trial has been performed to evaluate the potential for a single-stage Integra® reconstruction procedure in the burn population.

Furthermore, these studies, while encouraging, were performed with standard Integra®. A thinner version of Integra®, which is half of the thickness of standard Integra®, has been developed for ease of use in trickier anatomic areas, such as the axilla, where increased flexibility would be useful. We believe this decreased thickness would be useful in a single-stage reconstruction, as skin grafts initially receive nutrients prior to incorporation and new blood vessel growth via imbibition. While single-stage reconstruction with Integra® has been demonstrated with standard thickness Integra®, we believe this decreased thickness would increase the likelihood of graft survival due to the decreased distance of nutrient diffusion.

1.3 What preliminary results do you have that support your proposal?

Our burn center has examined the use of Integra® with autografting in a single-stage procedure in the setting of chronic wounds. In 2009, patients with chronic wounds refractory to treatment for more than 3 months in our wound clinic were considered for treated with Integra®. Six patients underwent a single-staged composite graft (Integra® + autograft). Of these six patients, all six had graft "take" classified as "good" at one week. Five of the six had graft take classified as "good" at one month, with the remaining patient's graft take classified as "fair". This was in the setting of chronic wounds, which are notoriously difficult to heal, typically due to patient comorbidities which impair vascularity of the wound beds.

1.4 What is the importance of the research to the scientific community?

Demonstrating the safety and feasibility of single-stage Integra® reconstruction could lead the way towards changing the standard of care for a significant population of burn patients, potentially reducing the hospital stays of thousands of patients each year.

****2. APPROACH****

Some questions in this section do not apply to all study designs; please mark Not Applicable as appropriate

2.1 Describe the study design (e.g., "This is a randomized controlled trial to test the effect of a guided imagery intervention on sleep quality"). Please see this List of Study Designs.

This is a prospective, descriptive, pilot case series involving patients with significant burns who are candidates for reconstruction with Integra®. Should they choose to participate in the trial, the majority of a patient's wounds would be treated in accordance with standard cares of the Regions Hospital Burn Center. However, a small area of the wound would, at the time of excision, have the smallest sheet of thin Integra® (125 cm²) placed and be immediately autografted with a 3:1 meshed split-thickness skin graft. Of note, 125 cm² represents approximately 0.7% of an average sized patient's total body surface area, so for even the smallest burns in our proposed trial, this area would represent a small portion of the patient's area of injury. The remaining injury areas would be covered with standard-thickness Integra® only. The donor graft, a 4 cm x 10 cm sheet of skin, would be meshed in a 3:1 ratio to be expanded to cover the 125 cm² sheet of thin Integra®. The patient's post-operative care would be largely unchanged, although the patient would have a donor site of 40 cm² that would be dressed and managed in the usual fashion.

Post-operatively, the patient's care would be largely unchanged. Progress of graft "take" at the single-stage 125cm² site would be monitored regularly. Eventually, 10-14 days later, the patient would return to the operating room for eventual auto-grafting over their standard Integra®. If autograft "take" at the single-stage site was poor, the area would be regrafted. If graft "take" at the single-stage site was adequate, the area would not require additional surgery. Thus, the total number of surgeries would not be expected to change, as the patient will require two trips to the operating room regardless of trial enrollment. The 125 cm² site would be monitored daily after dressing "take-down" (typically post-operative day 5) while hospitalized and then on a standard post-operative schedule for sloughing or graft loss, infection, hematoma or underlying blood collection, seroma or underlying fluid collection, and time to 95% healed. This last variable is measured by determining the post-operative day at which 95% of the surface area of the graft is covered with epidermis. Because we are meshing the 40 cm² sheet of skin in a 3:1 fashion, the resultant graft will look like a thin fence of skin with open diamond-shaped interstices that will slowly each fill in from the peripheral surrounding skin as the graft heals. It is these interstices that give the typical meshed appearance of healed skin grafts. When 95% of the open areas have filled in, that day is determined to be the time to 95% healing. Similarly, an adjacent area of identical size, which will be treated in the standard fashion, will be monitored serially and will serve as a control. Since patients will serve as their own controls, a direct comparison between reconstruction strategies will be enabled.

Not Applicable

Eligible patients will be adults (Age 18 or older) admitted to the Regions Hospital Burn Center with thermal burns that will be reconstructed with Integra®. There is not a firm protocol in place for Integra® use – this is decided at the level of the burn attending physician on a case-by-case basis.

2.3 What is the study population of interest and what are the study inclusion/exclusion criteria?

Inclusion criteria – English-speaking adult burn patients greater than 18 years old, admitted with burn injuries eligible for Integra® reconstruction at the discretion of the burn attending physicians.

Exclusion criteria – patients with isolated hand or face burns – these burns are treated with sheet grafts (unmeshed); the 3:1 mesh grafts would not be used on these cosmetically sensitive areas. If they have hand and/or face burns *in addition* to other areas, they will not be excluded. However, the study itself will not be performed on the hands or face. Additionally, patients unable to present to our clinic for routine follow-up due to geographic limitations or otherwise will be ineligible.

2.4 If you are not using the entire population of interest, what is the method for obtaining a subset or sample of this population?

Χ	Not Applicable

2.5 Will you need to perform "preparation for research" activities prior to consenting subjects for research?

X	No	
	Yes	
	Not	
	Applic	able

If you answered yes above, appropriate preparation for research activities prior to consenting subjects must include the following process to determine inclusion/exclusion criteria:

- 1) Study staff will work with the PI to determine the methods used in identifying potential subjects for the research. For example, this may include creating an Epic Workbench report of patients who are in the hospital and meet minimum criteria for the research.
- 2) Study staff may access medical records of all potential subjects' identified (i.e., Workbench) to determine eligibility criteria using information that already exists in the medical record. During this process, no identifiable information may be recorded and any documentation made of a potential subject's information that would disqualify them will be destroyed.

If an eligible patient is not being cared for by the PI, study staff must approach the patient's provider to determine if it is appropriate to proceed with the consent process.

- 3) If additional testing needs to be done to see whether a patient meets criteria for entry into the study, the PI or staff will need to consent the patient first.
- 4) If the preparation activity confirms a patient is a possible subject, PI/staff approaches the patient to begin the consent process.

2.6 Describe the steps in your recruitment process.

Not Applicable

Patients meeting inclusion criteria will be approached prior to their excision and Integra® placement procedure. The risks and benefits of the study will be discussed so that informed consent could be obtained.

2.7 Describe any interventions that are used in this study.

Not Applicable

Enrolled patients will undergo a single-stage reconstruction of 125 cm² of their burn – thin Integra® will be placed with an immediate split-thickness skin graft placed at the time of the first surgery. The remainder of their injury will be treated

according to the routine standard of care – first-stage excision and Integra® placement with second-stage autografting 10-14 days later.

2.8 Provide a brief, sequential, bullet-point description of the all the data collection activities you will conduct from start to finish (e.g., chart review, patient survey, follow-up visits, data pull from the electronic medical record, etc.) and who will conduct each. Please see our Example of Data Collection Steps.

After enrollment, we will collect

- -Age, gender, %BSAB, mechanism of injury, location of burns
- -presence of burn cellulitis
- -Post-burn day of Stage 1 of reconstruction (excision, Integra® placement, and 125 cm² auto-graft)
- -location of 125cm² single-stage reconstruction site
- -percentage of graft coverage at first dressing takedown, typically post-operative day 5 and then daily
- -post-burn day of Stage 2 of reconstruction (auto-grafting over remaining Integra®, re-grafting of initial 125 cm² study area if necessary.
- -time to 95% healing of single-stage grafted area and time to 95% healing of control 125 cm² wound auto-grafted during second reconstruction procedure adjacent to the single-stage graft.
- -single-stage graft site complications (infection, hematoma, seroma, sloughing of graft)
- -adjacent (control) wound complications (infection, hematoma, seroma, sloughing of graft)

2.9 Provide a timeline for the main study activities. Please see our **Example Timeline**

October, 2016 - IRB submission

December, 2016 – February, 2016 – patient enrollment

March, 2016 - April, 2016 - Data Collection/Analysis

May, 2016 – June, 2016 – Abstract/Manuscript preparation

